NON-INTERVENTIONAL (NI) STUDY PROTOCOL

Study information

Title	Safety and effectiveness of apixaban compared to warfarin in secondary prevention in patients with NVAF with a history of stroke or transient ischemic attack - a nationwide retrospective observational study using claims data in Japan
Protocol number	B0661176
Protocol version identifier	Ver.1.1
Date	24/3/2022
EU Post Authorization Study (PAS) register number	Not applicable
Active substance	B: Blood and blood forming organs B01: Antithrombotic agents B01A: Antithrombotic agents B01AF: Direct factor Xa inhibitors B01AF02: Apixaban
Medicinal product	Eliquis(Apixaban)
Research question and objectives	Japanese population has shown to have higher rate of incidence of stroke and stroke mortality is also higher ¹ . Patients with a history of ischemic stroke are at high risk of recurrence and require more rigorous management to prevent recurrence ² . The same is true for patients with non-valvular atrial fibrillation (NVAF) and treatment with anticoagulants reduces the risk of recurrent embolic stroke. However, some patients still suffer from recurrent embolic and/or ischemic stroke even if they are on anticoagulants for secondary prevention ³ . In addition to the recurrent stroke, risk of bleeding is also higher in the patients with a history of stroke because they are often chronically treated with antiplatelet agents to prevent recurrence after cerebral infarction and with an anticoagulant after embolic stroke ^{4,5} . Concomitant use of anticoagulant and anti-platelet agents is sometimes necessary if patients with AF experience cerebral infarction

	
and the risk of bleedings largely enhances in these patient⁶. Thus, patients in secondary prevention are at higher risk of both recurrent ischemic stroke and more effective and safer antithrombotic therapy should take this into account.
 
The purposes of this study are 1) to characterize the primary and secondary prevention patients, 2) to calculate incidence rates of stroke/SE or major bleeding in each cohort and 3) to investigate for Japanese secondary prevention patients as RWE on the effectiveness and safety of apixaban compared to warfarin in patients NVAF.

Author	PPD [REDACTED]

Contents

2. LIST OF ABBREVIATIONS.....	5
3. RESPONSIBLE PARTIES.....	5
4. ABSTRACT.....	6
5. FINAL REPORT APPROVAL.....	10
6. MILESTONES.....	11
7. RATIONALE AND BACKGROUND.....	11
8. RESEARCH QUESTION AND OBJECTIVES.....	11
8.1. PRIMARY OBJECTIVE:.....	12

1. LIST OF ABBREVIATIONS

Abbreviation	Definition
AF	Atrial fibrillation
COPD	Chronic obstructive pulmonary disease
DOAC	Direct oral anticoagulant
HAS-BLED	Not an abbreviation. Hypertension, Abnormal renal / liver function, Stroke, Bleeding, Labile INRs, Elderly, Drugs / alcohol
ICD-10	International classification of diseases-10
ICH	Intracranial hemorrhage
ID	Identifier
IEC	Independent ethics committee
IPTW	Inverse probability of treatment weighting
IRB	Institutional review board
MDV	Medical Data Vision Ltd.
NSAID	Non-steroidal anti-inflammatory drug
NVAF	Non-valvular atrial fibrillation
OAC	Oral anticoagulant
RWE	Real world evidence
SAP	Statistical Analysis Plan
SE	Systemic embolism
TIA	Transient ischemic attack

3. ABSTRACT

Title :

Safety and effectiveness of apixaban compared to warfarin in secondary prevention in patients with NVAF with a history of stroke or transient ischemic attack - a nationwide retrospective observational study using claims data in Japan

Protocol Ver1.1 (24-Mar-2022)

PPD

Rationale and background :

Japanese population has shown to have higher rate of incidence of stroke and stroke mortality is also higher¹. Patients with a history of ischemic stroke are at high risk of recurrence and require more rigorous management to prevent recurrence². The same is true for patients with non-valvular atrial fibrillation (NVAF) and treatment with anticoagulants reduces the risk of recurrent embolic stroke. However, some patients still suffer from recurrent embolic and/or ischemic stroke even if they are on anticoagulants for secondary prevention³. In addition to the recurrent stroke, risk of bleeding is also higher in the patients with a history of stroke because they are often chronically treated with antiplatelet agents to prevent recurrence after cerebral infarction and with an anticoagulant after embolic stroke^{4,5}. Concomitant use of anticoagulant and anti-platelet agents is sometimes necessary if patients with AF experience cerebral infarction and the risk of bleedings largely enhances in these patient⁶. Thus, patients in secondary prevention are at higher risk of both recurrent ischemic stroke and more effective and safer antithrombotic therapy should take this into account.

Research question and objectives :

The pivotal randomized clinical trial, ARISTOTLE study⁷, and other RWE⁸⁻¹¹, in which medical and claims data have been retrospectively analyzed, have shown that the risks of incidence of stroke + systemic embolism and major bleeding in patients with NVAF treated with apixaban is equal to or lessor than those in patients treated with warfarin. As mentioned above, patients with NVAF and with a history of ischemic stroke (that is, in secondary prevention) could be at higher risk of recurrence and bleeding. Although neurologists generally use direct oral anticoagulants

(DOAC) for secondary prevention, a significant portion of the patients in secondary prevention are still treated with warfarin in Japan. The results of randomized trials have indicated that apixaban is superior to warfarin in reducing the risk of recurrence and/or bleeding with secondary prevention of stroke¹²⁻¹⁴. However, there is no clear evidence in Japanese patients with secondary prevention of stroke¹⁵. The research question of this study is whether apixaban is associated with lower risk of stroke (ischemic and hemorrhagic) and bleeding compared to warfarin in higher-risk secondary prevention patients as well.

The purposes of this study are 1) to characterize the primary and secondary prevention patients, 2) to calculate incidence rates of stroke/systemic embolism (SE) or major bleeding in each cohort and 3) to investigate for Japanese secondary prevention patients as RWE on the effectiveness and safety of apixaban compared to warfarin in patients NVAF.

[figure not shown]
Study design :

It is a non-interventional comparative observational study, in which patients who meet the study criteria are selected and aggregated from the patients registered in the Medical Data Vision (MDV) database.

Population :

Patients who are newly diagnosed with NVAF and initiate anticoagulation therapy with warfarin or apixaban. Among them, patients with prior diagnosis of stroke (ischemic or hemorrhagic) or transient ischemic attack (TIA) are secondary prevention patients and will be included in the secondary prevention cohort and those who have not diagnosed with stroke will be included in the primary prevention cohort as primary prevention patients. Patient selection and allocation to each cohort is shown in Fig.1 below.

Analysis step #1

Analysis step #2

[figure not shown]

Fig.1a and 1b: patient selection and summary of planned analyses

Variables :

- Prior diagnosis of stroke (before diagnosis with NVAF)

- Clinical and demographic characteristics of patients eligible for this study.
- Incidence of recurrent stroke (ischemic and hemorrhagic) during the follow-up period
- Incidence of any bleeding including intracranial hemorrhage, gastrointestinal bleeding or intraocular bleeding during the follow-up period
- Anticoagulants (warfarin, apixaban or others)
- Concomitant medicines (baseline or on the index date)
- Comorbid diseases (baseline or on the index date)

Data sources :

Medical Data Vision database

De-identified health claim data from 458 acute-care hospitals across Japan (as of Dec.22, 2021) available from the MDV (Tokyo, Japan, MDV) database. In brief, the MDV database comprises administrative data pertaining to approximately 38 million individuals managed in the inpatient and outpatient settings. Each patient is associated with a specific ID to which all inpatient and outpatient data are linked.

Study size :

In this study, eligible patients will be aggregated backward.

- The number of estimated patients;
- All registered patients: approximately 38 millions (2008-2021)
- Patients with ischemic stroke: 1.2 millions
- Patients with TIA: 98,887
- Patients with atrial fibrillation: 1.3 millions
- AF patients with a history of ischemic stroke: 226,000
- AF patients on warfarin: 251,000
- AF patients on apixaban: 237,000
- The number of patients who experienced recurrent ischemic stroke on warfarin or apixaban: unknown

Data analysis :

The detailed methodology for data analysis will be described in the Statistical Analysis Plan (SAP). Briefly,

As a first step, extracted patients will be divided into two cohorts, primary prevention cohort and secondary prevention cohort based on the previous diagnosis of stroke. Clinical and demographic characteristics will be compared with two cohorts at baseline and on the index date (date of the initiation of warfarin and apixaban) and incidence rates of stroke/SE and major bleeding per 1,000 person-years will be calculated during follow-up period. In addition, interaction analysis will be conducted to investigate an interaction between OAC (warfarin/apixaban) and presence or absence of the previous episode of stroke.

- As a second step, only secondary prevention cohort will be used for further analyses as follows, Crude (before IPTW) patient characteristics will be compared between warfarin and apixaban cohorts using appropriate methods (continuous variables: unpaired t-test or Mann-Whitney U-test, categorical variables: chi-square test)
- A propensity score will be calculated based on multinomial logistic regressions in order to account for confounding effects and to ensure that patient characteristics will be balanced between the warfarin cohort and apixaban cohort. An inverse probability of treatment weighting (IPTW) method using the calculated propensity score will be applied. To avoid sample size inflation and to ensure appropriate estimation of variances, s-IPTW (stabilized IPTW) will be used here.
- Balanced (after IPTW) patient clinical and demographic characteristics will be shown. Covariate balance between apixaban and warfarin cohorts after s-IPTW will be assessed in terms of the standardized differences with a threshold of 0.1.
- Kaplan Meier curves of balanced cohorts for each endpoint will be drawn.
- Incidence rates of endpoints will be calculated and shown per 1000 person-year.
- Hazard ratios with 95% confidence intervals will be calculated using a Cox proportional hazards regression model that incorporate only the index OACs as independent variables.

Milestones :

- Data extraction start: Apr 15, 2022
- End of data extraction: Jun 30, 2022
- Final report approval: Aug 30, 2022

4. FINAL REPORT APPROVAL

Amendment number	Date	Protocol section(s) changed	Summary of amendment(s)	Reason

Ver 1.1	25/Mar/ 2022	5. Milestones	Change Data Extraction Date Before: Apr 1, 2022 After: Apr 15, 2022	To adjust the project schedule

5. MILESTONES

Milestone	Planned date
<Completion of feasibility assessment>	October 14, 2021
Start of data collection	April 15, 2022
End of data collection	Jun 30, 2022
Final study report	Aug 30, 2022

6. RATIONALE AND BACKGROUND

Patients with a history of ischemic stroke, including those with cardiogenic cerebral embolism, are at higher risk of recurrence and require more rigorous treatment to prevent recurrence. The same is true for patients with non-valvular atrial fibrillation (NVAF), who are at higher risk of recurrence even if they are taking anticoagulants to prevent cardiogenic cerebral embolism. On the other hand, NVAF patients with previous lacunar infarction are often chronically treated with antiplatelet agents to prevent recurrence, and this could result in an increased risk of bleeding. Thus, patients in secondary prevention are at higher risk of recurrent stroke (both ischemic stroke and hemorrhagic stroke) and bleeding than those in primary prevention, and antithrombotic therapy should take this into account.

7. RESEARCH QUESTION AND OBJECTIVES

The pivotal randomized clinical trial, ARISTOTLE study, and other RWE, in which medical and claims data have been retrospectively analyzed, have shown that the risks of incidence of stroke + systemic embolism and major bleeding in patients with NVAF treated with apixaban is equal to or lessor than those in patients treated with warfarin. As mentioned above, patients with NVAF and with a history of ischemic stroke (that is, in secondary prevention) could be at higher risk of recurrence and bleeding. Although neurologists generally use direct oral anticoagulants (DOAC) for secondary prevention, a significant portion of the patients in secondary prevention are still treated with warfarin in Japan. There is no clear evidence that apixaban is superior to warfarin in reducing the risk of recurrence or bleeding in Japanese patients with secondary prevention of

stroke. The research question of this study is whether apixaban is associated with lower risk of stroke (ischemic stroke and hemorrhagic stroke) and bleeding compared to warfarin in higher-risk secondary prevention patients as well.

7.1. Primary objective:

The effectiveness of study in secondary prevention cohort will be conducted to elucidate the following,

1. Incidence rate (per 1,000 person-years) of a composite of recurrent stroke (ischemic stroke and hemorrhage stroke) in NVAF patients treated with warfarin or apixaban.
2. Time course of proportion of a composite of the incidence of recurrent stroke (ischemic stroke and hemorrhage stroke) -free NVAF patients treated with warfarin or apixaban (shown as two Kaplan-Meier curves, for warfarin cohort and apixaban cohort, which will be statistically compared by a Log-rank test).
3. Risk of a composite of recurrent “Ischemic stroke” (“cardiogenic cerebral embolism” + “cerebral infarction”) and hemorrhagic stroke and SE in patients treated with apixaban compared to that in patients treated with warfarin (Hazard ratio and 95% confident intervals will be calculated by a COX proportional hazard method) (**primary effectiveness analysis**).

* TIA is not included in endpoints.

The safety of study will be conducted to elucidate the following,

1. Incidence rate of recurrent bleeding, such as major bleeding, intracranial hemorrhage, gastrointestinal tract bleeding or intraocular bleeding in NVAF patients treated with warfarin or apixaban
2. Time course of proportion of each bleeding-free in NVAF patients treated with warfarin or apixaban (shown as two Kaplan-Meier curves, for warfarin cohort and apixaban cohort, which will be statistically compared by a Log-rank test).
3. Risk of each bleeding in NVAF patients treated with apixaban compared to that in patients treated with warfarin (Hazard ratio and 95% confident intervals will be calculated by a COX proportional hazard method) (**primary safety analysis**).

In summary,

[figure not shown]
- **Primary effectiveness endpoint** : stroke (ischemic stroke and hemorrhage stroke)/SE

- **Secondary effectiveness endpoints:**
 - Recurrent cardiogenic embolic stroke
 - Recurrent cerebral infarction
- **Primary safety endpoint** : major bleeding defined as any bleeding requiring hospitalization for treatment
- **Secondary safety endpoints:**
 - Intracranial hemorrhage
 - Gastrointestinal bleeding
 - Intraocular bleeding

8. RESEARCH METHODS

8.1. Study design

This is a non-interventional, comparative, observational study in which patients registered in the MDV database who met the study criteria are retrospectively aggregated. This is a secondary collection database study, and no primary data collection will be done.

8.1.1. Definition 1

8.1.1.1. Index date

The next day of the day when patients diagnosed NVAF initiate warfarin or apixaban

8.1.1.2. stroke

8.1.1.3. Defined using pre-designated ICD-10 codes (see Statistical Analysis Plan). Ischemic and hemorrhagic stroke will be included,stroke

Stroke is defined using predefined ICD-10 codes and if hospitalization for the treatment of the stroke is necessary, it will be regarded as stroke incident during the followup period.
(applicable only to the outpatients when recurrent stroke occurs)

8.1.1.4. Major bleeding

Major bleeding is defined any bleeding that needs hospitalization for the treatment of bleeding. Any bleeding is defined using pre-designated ICD-10 codes (see Statistical Analysis Plan).

8.1.1.5. Other clinical critical bleeding

Intracranial hemorrhage, gastrointestinal tract bleeding or intraocular bleeding

8.1.1.6. Baseline period

Period of 180 days before the index date.

8.1.1.7. Follow up period:

The end of observation is the period until the first observation of the earlier of the following items.

1. discontinuation of the index OAC (warfarin or apixaban, OAC prescribed on the index date); the index treatment is considered to be discontinued if there is a continuous gap of 45 days or more between the expected refill date and the actual refill date.
2. switch to another OAC; the index treatment is regarded as switched if the index OAC was discontinued and another OAC was started within 45 days of the prescription refill date of the index OAC.
3. lack of further records in the database; if no further relevant records are added (e.g., no further refills or visits), the last date of the patient's record in the database is considered.
4. occurrence of stroke or major bleeding (endpoints).
5. elapsing of 2 years from the index date.

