### 2.1.3. Treatment/cohort labels

Step-1

1. Primary prevention patients who are newly diagnosed with NVAF and initiated warfarin or apixaban (primary prevention cohort)
2. Secondary prevention patients who are newly diagnosed with NVAF and initiated warfarin or apixaban (secondary prevention cohort)

Step-2

1. Balanced Warfarin cohort of secondary prevention (warfarin cohort)
2. Balanced apixaban cohort of secondary prevention (apixaban cohort)

Patients will be assigned to each cohort based on the first prescription of oral anticoagulants after the diagnosis of NVAF (warfarin or apixaban). If the first oral anticoagulant prescribed was other than warfarin or apixaban or no oral anticoagulant was used, the patients will be excluded. Patient clinical and demographic characteristics will be balanced by using an IPTW method.

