#### **4.1.2. Exclusion criteria**

*Patients who meet the following exclusion criteria will be excluded from this study*

1. *Patients with a diagnosis of valvular AF (standard disease code: 8846941), postoperative AF (8847772), AF associated with mechanical valve malfunction (T82.0), mechanical complication of heart valve prosthesis (T82.0), or rheumatic AF (I05-I09) during the baseline period\*\*.*
2. *Patients with a diagnosis of VTE during the baseline period*
3. *Patients who are prescribed any anticoagulant during the baseline period.*
4. *Patients who are prescribed anticoagulants other than warfarin and apixaban on the index date*
5. *Patients who were hospitalized for more than 6 months (including index date) regardless of reason for hospitalization.*

*\*\*: maximally 6 months prior to the index date. If sufficient patient information is available for the analysis, patients who cannot have a 6-month baseline period will be included in the analysis.*

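### The switch rule does not end follow-up when another oral anticoagulant is started, so temporary or overlapping use of another OAC is counted as index-drug exposure, and no end date is given for permanent changers

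*Protocol*

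**What the plan says.** Protocol 8.1.1.7 lists five items that end observation, and the earliest applies: "The end of observation is the period until the first observation of the earlier of the following items". Three of them matter here.

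- Item 1, discontinuation of the index OAC: "there is a continuous gap of 45 days or more between the expected refill date and the actual refill date".
- Item 2 sets the condition for a switch: "switched if the index OAC was discontinued and another OAC was started within 45 days of the prescription refill date of the index OAC".
- Item 5, the cap: "elapsing of 2 years from the index date".

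The SAP does not restate or refine these rules. Cohort membership is fixed at the start (SAP 2.1.3): "Patients will be assigned to each cohort based on the first prescription of oral anticoagulants after the diagnosis of NVAF". The exclusions for other anticoagulants (SAP 4.1.2) concern the baseline period and the index date: "Patients who are prescribed anticoagulants other than warfarin and apixaban on the index date". SAP Appendix 1 on data derivation is marked not applicable. The only sensitivity analysis (SAP 7.2.1) is the E-value.

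**The concern.** Follow-up is on-treatment, and the Cox model contains the index OAC as its only independent variable (Protocol 8.7). Person-time and events are therefore attributed correctly only if follow-up stops when the patient is no longer on the index drug alone. Item 2 joins two conditions with an 'and', so starting another OAC does not end follow-up by itself.

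Three terms are also left open:

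- whether the prescription refill date is the last actual refill or the expected next one;
- whether the 45-day window runs only forward from that date or to both sides of it;
- on what date a discontinuation or a switch ends observation.

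If the other OAC is apixaban and the index drug is warfarin, comparator time and events go to the wrong arm. The same follow-up rule feeds the primary effectiveness analysis, the primary safety analysis and the Step 1 incidence rates. The E-value addresses unmeasured confounding and says nothing about misclassified exposure.

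**Working it through.** The plan states no figure that depends on this rule, so there is none to reproduce. The check has two parts.

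**1. Items 1 and 2 applied case by case**, with discontinuation as item 1 defines it.

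*Change and return.* Suppose warfarin supply ends on day 30, another OAC is taken on days 30 to 70, and warfarin is refilled on day 70. The gap is 70 − 30 = 40 days, below 45. Item 1 is not met, so item 2 is not met either. All 40 days, and any endpoint in them, count as warfarin.

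*Overlap.* Another OAC is added while the index drug is refilled on time. There is no gap, so neither item is met. Overlapping time counts as index exposure, potentially up to the 2-year cap.

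*Permanent change mid-supply.* The index drug is not refilled, the gap reaches 45 days, and item 1 ends observation. With s days of supply left at the change, the time on the other OAC credited to the index drug depends on the end date chosen:

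| End dated at | Days credited | s = 30 (assumed: 90-day supply, change on day 60) |
|---|---|---|
| start of the new OAC | 0 | 0 |
| end of index supply | s | 30 |
| day 45 of the gap | s + 45 | 75 |

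The documents do not choose among these rows.

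**2. Possible size.** Inputs:

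- True HR 0.65, the value expected in SAP 7.2.2.
- Assumed, because the documents give no switching rate or supply length: 20% of warfarin patients change per year, with 30 to 90 days misattributed for each.
- Assumed rate in the misattributed time, r, relative to the warfarin rate: 0.65 (the apixaban rate) or 3.

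Misattributed share of warfarin time:

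- f = 0.20 × 30/365 = 1.6%
- f = 0.20 × 90/365 = 4.9%

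Observed HR = 0.65 / [(1 − f) + r f]:

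| | f = 1.6% | f = 4.9% |
|---|---|---|
| r = 0.65 | 0.65/0.9942 = 0.654 | 0.65/0.9827 = 0.661 |
| r = 3 | 0.65/1.0329 = 0.629 | 0.65/1.0986 = 0.592 |

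At r = 1 the observed HR stays at 0.65, so the direction depends on whether the rate around a change is below or above the warfarin rate.

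A wider assumption lets a share g of apixaban time carry the warfarin rate as well: observed HR = [0.65(1 − g) + g] / [(1 − f) + 0.65 f].

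- f = 1%, g = 0: 0.65/0.9965 = 0.652
- f = 10%, g = 0: 0.65/0.965 = 0.674
- f = g = 10%: 0.685/0.965 = 0.710

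**The case against.** The best counter-argument is that the strict reading leaves item 2 little to do. If a switch needs item 1's full gap, item 2 adds no patient whom item 1 does not already end. Discontinued in item 2 may therefore simply mean stopped. On that reading the change-and-return example is a switch on day 30, because the other OAC starts on the expected refill date. Claims data are also read in retrospect, so the gap can be confirmed later and the switch dated back to the new start. The text does not exclude this, and it sets no order between the two conditions.

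This objection stands in part. It shows that the rule is ambiguous, but it does not repair the rule. Item 1 defines the term immediately above item 2. Even on the looser reading, overlapping use is not covered, the refill date is undefined and no end date is given.

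A reader might also infer that everyone who changes drug mid-supply stays labelled with the index drug. The documents do not support that: a permanent changer meets item 1, and the misattributed time is bounded by s + 45 days and may be zero.

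Nor does the remark in the Protocol abstract that "a significant portion of the patients in secondary prevention are still treated with warfarin in Japan" show that switching is common. It describes how many patients take warfarin, not how many leave it.

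**Conclusion.** The point holds as a defect in a stated exposure rule. Under item 1's definition, change-and-return within the gap and overlapping OAC use are credited to the index drug. No other text in the protocol or SAP ends follow-up at the start of a non-index OAC. For permanent changers the defect is narrower: the missing end date.

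The size cannot be derived from the documents. Every input except the HR of 0.65 is assumed, and no frequency is available for change-and-return or overlap, the two cases that the rule handles worst. The HR values of 0.63 to 0.59 rest entirely on the assumed tripling of the event rate around a change. It would go too far to conclude that the primary hazard ratios are materially biased, or biased in a known direction. The effect is probably modest. The rule should still be corrected, because it enters both primary analyses and two programmers could derive different person-time from the same text.

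**What to change.** Replace item 2 in Protocol 8.1.1.7, and add the same text to the SAP:

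*Switch: the first dispensing after the index date of any OAC other than the index OAC, whether or not the index OAC supply has run out or is later refilled; follow-up ends on that date.*

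This drops both the prior-discontinuation condition and the 45-day window for switches. It settles all three cases and removes the undefined refill date from item 2. Two additions are needed:

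- State the end date used for item 1 (end of supply, day 45 of the gap, or another stated date).
- State that an endpoint on the same day as the new dispensing counts as an event under the index OAC. Otherwise, an event that prompts the change could be lost to censoring.

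The cost is a few sentences in each document and a simpler program. A few patients with a stray or duplicate prescription of a second OAC would be censored early, with a small loss of person-time. The change concerns only how existing claims data are classified and affects no patient's care. It settles attribution only: censoring at a switch may still be informative, as in any on-treatment analysis.
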